Time to Hemostasis (TTH) is defined as the time period required to achieve hemostasis, more specifically the time during which the subject is wearing the HMS system and the system is active, e.g. applying compressive force to the access site. For clarity, the time period that a HMS is left on the wrist while totally deflated is not considered as part of the TTH time.

IV. STUDY DESIGN AND METHODOLOGY

STUDY DESIGN

This study is a physician initiated, prospective, observational, two arm, randomized study to be performed at up to four experienced 'Radial First' centers. A minimum of 120 patients having undergone successful radial catheterization will be enrolled in the study, 60 in each arm.

Enrollment will continue at each site on discretion of the investigators until each center enrolls a minimum of 30 patients, or a maximum of 180 patients are enrolled. Clinicians will perform the catheterization in accordance with local standard practice, with a minimum of 5,000 units of unfractionated heparin for anticoagulation.

STUDY METHODS:

Patient Selection Criteria Study subjects will be identified in the catheterization laboratory holding area and asked to sign the informed consent prior to their catheterization procedure before the administration of sedative agents.

Inclusion Criteria:

- Patient undergoing diagnostic angiography or PCI via the radial artery
- Patients with a Barbeau test prior to the procedure showing pattern A,B,or C.

Exclusion Criteria:

Candidates for this study will be excluded if any **one** of the following criteria is true.

- Use of a radial sheath larger than 6 Fr (a 7Fr-in-6 Glidesheath Slender[®] is allowed).
- Use of an anticoagulant other than unfractionated heparin or bivalirudin.

- Any anticipated need for continued anticoagulation post-catheterization. Glycoprotein inhibitors are acceptable.
- Any active treatment with oral anticoagulants continued during course of procedure.
- Presence of arteriovenous dialysis fistula in the ipsilateral arm.
- Any physical deformity or trauma / injury of either wrist that would prevent proper placement or function of the hemostasis band.
- Raynaud's syndrome or known peripheral vascular disease of the forearm.
- Mental incompetence or inability to follow the instructions to complete the study.
- History or presence of Radial Artery Occlusion.
- Barbeau test showing Pattern D.
- Patients undergoing catheterization from the femoral or ulnar artery approach.

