- Cardiogenic shock or any clinical instability as assessed by the physician performing the procedure.

Transradial Catheterization Procedure

Transradial Cardiac Catheterization will be performed according to local practice standards with use of a sheath diameter of up to 6 Fr. (A 7Fr-in-6 Glidesheath Slender®, with an outer diameter of 6Fr is defined as a 6F sheath and is allowed.) In accordance with current recommendations for minimizing radial artery occlusion, a minimum of 5,000 units of unfractionated heparin, or therapeutic bolus of bivalirudin, will be administered to all patients enrolled in the study.

Patients will have their activated clotting time measured at least 5 minutes following the initial dose of anticoagulant, although every patient receiving 5,000 units of heparin will be eligible for the study. Vasodilators (nitroglycerin, verapamil) will be administered in accordance with local practice.

Timing of Subject Enrollment

A subject will be consented into the study prior to the administration of sedation prior to the procedure, and randomized at the conclusion of a successful procedure (after all anticoagulation and antiplatelet medication decisions have been made), at which time placement of the assigned HMS device will occur. Eligibility for the study will be assessed at this time and the subject will have to meet all of the inclusion criteria and none of the exclusion criteria.

Randomization will be performed by means of sealed envelopes in randomization blocks of 30. Each envelope will be labeled by patient number containing device designation. Device designation in the envelopes will be random in occurrence. When a patient is officially enrolled (after successful completion of a TRA procedure), the envelope corresponding to that patient number in the Study Patient log will be pulled, opened, and the assignment revealed.

Each of 4 sites will be allotted an initial block of 30 envelopes, and sets of backup blocks of 30 envelopes. On the discretion of the site principal investigator and the lead principal investigator, enrollment may continue until each site enrolls 30 patients. The maximum enrollment at any one site shall not exceed 50% of the total study enrollment, or 90 patients.

End of Study Status / Effect of Withdrawals:

A subject will have completed the study when one of the following events is documented:

1. The patient is successfully enrolled, treated with a HMS, and completes all required follow up tests.

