2. A subject withdraws consent to participate. Patients who withdraw from the study will be replaced and excluded from data analysis.

[figure not shown]
Protocol:

Control patients: Patients will have a TR band applied over the arteriotomy site and inflated with 15-18ml of air. After aspirating and clearing the contents of the sheath, the radial sheath will be removed. The TR band will be deflated until bleeding occurs, and 2 ml of air will be reintroduced to provide hemostasis. Patent hemostasis will be documented with plethysmography and oximetry as described below within 5 minutes after band application and removal, and within 30 min of discharge or after 24 hours. The TR band will be left inflated and in place for 2 hours following the procedure for all patients (regardless of diagnostic or PCI procedure), after which deflation attempts will commence.

Statseal Protocol: Patients will have a Statseal Advance (SSA) disc applied after withdrawing the radial sheath 2-4 cm. A Tegaderm dressing will be applied to secure the disc position. The TR band will be applied over the SSA disc with the center of the balloon (the green dot) over the center of the SSA disc. The TR band will be inflated with 8cc of air (which is typically occlusive pressure), and the sheath removed. No deflation will occur immediately. After 20 minutes of pressure, 3 cc of air will be removed from the TR band. After an additional 20 minutes (40 minutes after procedure), the TR band will be completely deflated, and the TR band left in place. After an additional 20 minutes (60 minutes after procedure) the TR band will be removed.

[rest of page intentionally blank]

STUDY OVERVIEW GRAPHIC

V. STUDY ACTIVITIES & GUIDELINES

Inspection Prior to Use

Prior to initiating any study activities, inspect the HMS devices for any damage. Do not use any device that appears compromised or damaged.

Required Accessories for each experiment

- Hemostasis Band (TR Band, Terumo, Inc.)
- StatSeal Advanced disc (if randomized to test group)
- Pulse oximeter

ACTIVITIES AND ASSESSMENTS

Informed Consent:

Subjects must have read the contents of the written informed consent document, had all questions regarding the study adequately answered by study staff, and signed and dated the document prior to any study related activities. See Appendix 1 for a sample of the Informed Consent document.

Definitions of Baseline and Procedural Variables:

Smoking: Active smoking or >20 pack year tobacco history.

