The sample size of 120 patients is estimated to have 90% power to detect an average difference in time to removal of the TR band of 60 minutes between the SSA and TRB groups, using a relatively large standard deviation of 100 minutes and a two-sided alpha of 0.05.

Descriptive summary statistics will be presented for all study variables. Continuous variables will be displayed as means with standard deviations and medians with 75th and 25th percentiles. Categorical variables will be summarized as frequencies with their respective percentages with two-sided 95% exact confidence intervals of the percentages. Statistical comparisons for continuous variables will be performed using the Student's t test or Mann-Whitney U test, as appropriate. Comparisons for categorical variables will be performed using the Chi square test or Fisher exact test, as appropriate. A two-sided P value of 0.05 will be considered statistically significant.

Categorical variables will include, but are not limited to:

- Percent of patients in each arm with total TTH of 60 minutes or less.
- Percent of patients in each arm with TTH of 40 minutes or less without complication.
- The percentage of patients in each arm with bleeding, oozing or hematoma during TTH, further delineated by the EASY bleeding and hematoma classification attached.
- Percent of patients in each arm with RAO at each /all follow-up points.
- Percent of patients in each arm with radial patency as tested with Pleth-ox at each designated test time point.

Primary Efficacy Outcomes:

In each arm the:

- Total Time to Hemostasis (TTH), defined as the total time the HMS applies compressive force until successful hemostasis is achieved without complication.

Secondary Efficacy Outcomes:

In each arm the:

- Percent of patients free from radial artery occlusion at discharge or at 24 hours, whichever occurs first.
- Percent of patients with Barbeau test patterns A,B,C,D at initial application of the HMS
- Percent of SSA patients with Barbeau test patterns A,B,C,D after 20' of HMS time.
- Percent of patients with Barbeau test patterns A,B,C,D at full deflation of the HMS. (40' for SSA group; per protocol in the TRB group)
- Percent of patients with Barbeau test patterns A,B,C,D at discharge or at 24 hours, whichever occurs first.
- Percent of patients in whom successful hemostasis is achieved in one hour or less.

Primary Safety Outcome:

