Each subject in the study must sign the informed consent agreeing to participation.

Alternatives to Participation

As a voluntary randomized study, the patient's alternative to participation is primarily to the local standard of care, typically involving the TR band, used per local protocol (typically 1-3 hours of application). SSA devices may be used outside of the study depending on local practice and availability.

Study Activities

The Investigator is required to perform the study in accordance with the protocol and to use the HMS per the instructions for use.

Follow-Up

There is no requirement for the subjects taking part in the study to be seen or examined for any follow up relative to the study following completion of activities described herein.

CRFs

CRFs will be completed for each subject. See Appendix 1 for the CRFs.

Records and Retention

Copies of all records will be retained by the investigator at each site for 2 years.

(Model) Patient Informed Consent

See Appendix 2 for a model of the informed consent.

Communication with the Principal Investigator:

All communication regarding the study should be routed directly to the Principal Investigator.

Copies of all correspondence regarding the study should be maintained in the Site Investigator study file.

Declaration of Helsinki & HIPPA

The Principal Investigator will ensure that this study is performed in conformity with the Declaration of Helsinki, HIPPA, and all local and national regulations.

Investigator Responsibilities

- Sign and adhere to the Investigator Agreement
- Sign and adhere to all of the required elements of the Clinical Protocol
- Resolve queries in a timely manner
- Participate in Investigator meetings, if scheduled
- Comply with the Declaration of Helsinki
- Obtain written Informed Consent from each study participant before any study specific procedures are performed
- Complete all required case report forms (CRFs) for each subject
- Comply with all applicable regulations and codes of approvals from the site IRB and other Regulatory Authorities
- Notify the Principal Investigator of personnel changes that may affect the study protocol
- Retain all records and study files as required, after which the files may be destroyed.
- Allow direct access to source data/documents, including patient records, in case of monitoring, auditing and/or inspection by the IRB and/or other regulatory authority bodies.

X. RISK BENEFIT ANALYSIS

General Risks and Presumed Benefits:

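### Envelopes are blocked by site but the TTH tests ignore site; if blocks are balanced, a site term would remove slight conservatism, with little effect on the result

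*Protocol*

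**What the plan says.** **Allocation** (Protocol IV, Timing of Subject Enrollment). "Randomization will be performed by means of sealed envelopes in randomization blocks of 30", and "Each of 4 sites will be allotted an initial block of 30 envelopes, and sets of backup blocks of 30 envelopes". On content, the text says only: "Device designation in the envelopes will be random in occurrence". The number of envelopes per arm in a block is not given.

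**Size** (Protocol IV, Study Design). "A minimum of 120 patients having undergone successful radial catheterization will be enrolled in the study, 60 in each arm". The study is a "randomized study to be performed at up to four experienced" centers, so the number of sites is a ceiling.

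**Analysis.** TTH is the primary efficacy outcome (Protocol VI). The protocol compares continuous variables by the t-test or the Mann-Whitney test. The SAP uses the unpaired t-test for means and the Mann-Whitney test for medians. No between-arm comparison includes site, and the SAP's only regression models predict hematoma.

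**Where site could enter.** In the StatSeal arm the schedule reaches full deflation at 40 minutes. In controls the band stays inflated for 2 hours "for all patients (regardless of diagnostic or PCI procedure), after which deflation attempts will commence", and the control-arm text gives no timetable from there. Protocol IX (Alternatives to Participation) describes usual care as "typically involving the TR band, used per local protocol (typically 1-3 hours of application".

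**The concern.** When allocation is balanced within sites, differences between sites cannot contribute to the difference between arms. An unpaired t-test does not know this. It leaves the between-site variation in its error term, so its standard error overstates the real uncertainty, its confidence interval is too wide and its p-value too large. A model with a site term takes that variation out.

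What is at stake is precision on the primary efficacy outcome, and standard errors that match the way patients were randomized. There is also a gap in reporting: without the arm split within a block, a reader cannot tell whether allocation was restricted within site at all.

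**Working it through.** **Inputs from the documents.** 60 per arm, difference 60 minutes, SD 100 minutes, two-sided alpha 0.05 (Protocol IV and VI); scheduled compression of 40 minutes against at least 120 (Protocol IV). The sample-size text refers to time to band removal; I apply its difference and SD to TTH.

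**Assumptions.** Four sites of 30, 15:15 in each, sites treated as fixed. Site mean control times lie between 120 minutes (the scheduled floor) and 180 minutes (the top of the usual-care range, which describes care outside the study).

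**Step 1: the plan's own figure.** n per arm = 2 × (1.960 + 1.282)² × 100² / 60² = 58.4, so 59 per arm and 118 in total. With 60 per arm, SE = 100 × √(2/60) = 18.26 minutes and 60/18.26 = 3.29; the noncentral t with 118 df gives 90.3% power. The stated 120 and 90% reproduce. For the scheduled gap of 120 − 40 = 80 minutes, power is 99.1%.

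**Step 2: site variance V.** Evenly spread offsets of −30, −10, 10 and 30 give V = (900 + 100 + 100 + 900)/4 = 500, or 5% of 100². Two sites at each end (−30, −30, 30, 30) give V = 900, or 9%.

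**Step 3: what each analysis uses as error variance** (total SD 100 in each arm).
- Unadjusted: about 10,000.
- Site acts on controls only: the variance that really applies, averaged over arms, is 10,000 − V/2. A model with arm and site gives half of each offset to each arm and leaves V/4 behind, so it uses 10,000 − V/4.
- Site acts equally on both arms: the applicable and the modelled variance are both 10,000 − V.

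The SE ratio is √(unadjusted / site-model variance). Type I error is 2 × P(Z > 1.96 × √(variance used / variance that applies)). Power for 60 minutes is Φ((60 − t × SE used) / SE that applies), with t = 1.980 (118 df) or 1.981 (115 df).

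| Case | SE ratio | Type I error, unadjusted / with site | Power, unadjusted / with site |
|---|---|---|---|
| Controls only, V = 500 | √(10,000/9,875) = 1.006 | 4.7% / 4.9% | 90.7% / 90.9% |
| Controls only, V = 900 | √(10,000/9,775) = 1.011 | 4.5% / 4.7% | 90.9% / 91.3% |
| Both arms, V = 500 | √(10,000/9,500) = 1.026 | 4.4% / 5.0% | 91.0% / 91.8% |
| Both arms, V = 900 | √(10,000/9,100) = 1.048 | 4.0% / 5.0% | 91.5% / 92.8% |

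Simulation gives SE ratios of 1.006 and 1.011 to 1.012 (controls only), and 1.026 to 1.027 and 1.049 (both arms). The 95% half-width of 1.980 × 18.26 = 36.2 minutes falls to 35.9 or 35.8 minutes (controls only) and to 35.2 or 34.5 minutes (both arms).

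**Step 4: a smaller SD.** The protocol sizes the study "using a relatively large standard deviation of 100 minutes and a two-sided alpha of 0.05". At an assumed SD of 50, controls only, the ratios are √(2,500/2,375) = 1.026 and √(2,500/2,275) = 1.048, but power is about 100% either way.

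**Step 5: what adjusting can cost.**
- No site effect, four full balanced blocks: no measurable cost.
- No site effect, sites of 60/30/20/10 with part-used blocks: SE about 0.4% larger with site.
- No site effect, assignment not blocked: simulated power 90.5% unadjusted, 89.6% with site.
- Site effect of 5% of variance in controls only, assignment not blocked: SE 0.6% larger with site, power 90.4% against 89.8%.

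**The case against.** The strongest reply is that nothing here is an error. The unadjusted t-test and the Mann-Whitney test are valid for this design, and in the case closest to the documents the gain is 0.2 to 0.4 power points. Even that case borrows its 180-minute end from care outside the study, whereas the study fixes 2 hours for every control; no document gives a between-site difference in TTH. The larger gains need site to shift both arms, although the StatSeal schedule is scripted. The 15:15 split is inferred, and without it adjusting can lose power. All of this stands. It limits the size of the point and makes the fix conditional on balanced blocks.

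A second reply concerns the form of the test. The scheduled times suggest skewed data: a normal StatSeal arm with mean 40 and SD 100 would put P(Z < −0.4) = 34% of times below zero. That is a good reason not to demote the Mann-Whitney test. A site-stratified rank test is no clear improvement, since in the controls-only simulations it lost about 0.5 to 1 point of power. In a further simulation with skewed times (StatSeal 40 minutes plus an exponential of mean 15; controls 120 minutes plus site offsets of 0 to 60 and an exponential of mean 10 to 100), every p-value from the t-test, the site model and the Mann-Whitney test was below 10⁻¹². No decision changed.

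A third reply is that the SAP is written in the past tense, so the analysis may be finished. That changes how a site-adjusted result should be labelled, not whether it is informative.

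**Conclusion.** The point holds as a small matter of precision, worth considering and no more. If blocks are 15:15 and site predicts TTH, the t-test's SE is about 0.6 to 1.2% larger than the site model's when site acts only on control weaning, and about 3 to 5% larger when the same offsets act on both arms. These figures rest on SD 100, four equal sites and an assumed 120 to 180 minute spread. If site does not predict TTH, there is no gain.

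A reader might infer three stronger things that the documents do not support:
- **That ignoring site inflates false positives.** With balanced blocks the unadjusted type I error is below 5% if site matters; with unblocked assignment it stays near 5%.
- **That the study is underpowered.** The 90% reproduces at 90.3%, and the scheduled gap of at least 80 minutes has 99.1% power at SD 100. The TTH conclusion is unlikely to turn on this.
- **That allocation is known to be balanced within site.** The protocol gives the block size and its issue by site, but not the arm split.

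Nothing is claimed here about power for radial artery occlusion or complications.

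**What to change.** 1. State in the protocol or SAP how many envelopes of each arm are in a block of 30.
2. If blocks are balanced, replace the unpaired t-test of mean TTH with a linear model containing arm and site, and report the unadjusted t-test as a sensitivity analysis. Keep the Mann-Whitney test as the planned rank test, and Fisher's exact test for occlusion and complications.
3. If blocks are not balanced, keep the unadjusted t-test.
4. If the analysis has already been done, report the site-adjusted model as a labelled post hoc sensitivity analysis.

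**Cost.** One or two sentences and no new data, because the site number is part of each patient study number (Protocol VIII, Data Confidentiality). With four sites the model spends 3 degrees of freedom. It costs about 0.4% in SE if site has no effect and sites are unequal, and up to about 1 power point if it is used although blocks are not balanced, which is why item 1 comes first.

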Diabetes: Hgb A1C >6.5% or active medical treatment for diabetes.

Hypercholesterolemia: LDL >130 or on treatment with antilipemic agents.

Hypertension: >140/80 or on medical treatment for hypertension.

Diagnostic procedure: Involving diagnostic catheters only.

Interventional procedure: Involving an interventional wire and therapeutic ACT typically >200, including for fractional flow reserve measurement where a stent is not placed.

Single wall puncture: Use of micropuncture wire and anterior wall puncture only.

Double wall puncture: Use of double wall puncture and sheath withdrawal technique.

Number of forward attempts: Number of forward advancements of the needle required to obtain access (not number of separate punctures of skin).

Procedure Start Time: Time when lidocaine is administered, prior to first puncture attempt.

Procedure End Time: Time when sheath is removed.

Test methodology:

All Pleth-ox testing will be done by qualified personnel with results classified according to Barbeau test pattern classifications. [Barbeau, et al. *Evaluation of ulnopalmar arterial arches with pulse oximetry and plethysmography; comparison with the Allen's test in 1010 patients. Am Heart Journal; 2004; 147:489-493*]

At the start of the TRA procedure, prior to radial artery cannulation, a baseline Pleth-ox exam will be performed for all patients and recorded on the CRF. Ulnar compression will be applied to confirm that the radial artery is patent. Patients with a type D pattern exam will be excluded from the study.

At the conclusion of a successful transradial procedure, the patient will be randomized to either SSA or TRB, each device applied per protocol & IFU.

Following placement of the HMS system, Pleth-Ox exams will be performed at the following time points with results recorded in the CRFs.

- Within 5 minutes of initial HMS placement
- In the SSA (StatSeal Advanced) group, within 5 minutes of the first partial deflation (20 minutes after initial placement).
- Within 5 minutes of full deflation of the HMS in both groups
- Within 30' of discharge or 24 hours post procedure (\pm 1 hour), whichever occurs first.

VI. STUDY STATISTICAL PLAN:

This is a physician initiated, prospective, randomized, two-arm study, to be conducted at up to four experienced 'Radial First' centers with the principal investigator having a (minimum) ten case experience using StatSeal Advanced.

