Any adverse event / complication at the vascular access site (e.g. Class III, IV, or V Hematoma,

other bleeding) at any time pre-discharge / at 24 hours other than RAO (as defined in the protocol).

Secondary Safety outcomes:

Any minor adverse event / complication (e.g. class I or II Hematoma) at the the vascular access site any time pre-discharge / at 24 hours other than RAO (as defined in the protocol).

Any complication (e.g. those typically associated with a PCI procedure) other than at the vascular access site at any time pre-discharge / at 24 hours other than RAO (as defined in the protocol).

VII. ADVERSE EVENTS:

Reports of all adverse events will be made and recorded for the duration of the study, and categorized as specific to those complications associated with radial access, such as hematoma, bleeding, RAO, and other vascular access complications, or those more typically associated with PCI, such as Major Adverse Cardiovascular Events (MACE).

Adverse events will be recorded on CRFs and adjudicated by the site Principal Investigator as to their severity and whether or not directly, indirectly, or not connected to the study HMS devices, and forwarded to the Data Center for entry in to the database.

DEFINITIONS:

Adverse Event

Any clinically relevant event that occurs during the performance of the study that puts the Subject at additional risk of injury, whether foreseen or not, and requires additional care beyond that expected as a result of the study.

Adverse Device Event

An adverse event related to the use of the device. This includes adverse events resulting from insufficient or inadequate instructions for use, deployment, or operation, or any malfunction of the device. This definition also includes any event resulting from user error or from intentional misuse of the device by the investigator.

Serious Adverse Event

A serious adverse event (SAE) is defined as an adverse event that:

- Led to death,
- Led to a serious deterioration in health that either,
 - Resulted in a life-threatening illness or injury, or
 - Resulted in a permanent impairment of a body structure or a body function, or
 - Required in-patient hospitalization, or
 - Resulted in medical or surgical intervention to prevent life threatening illness or injury or permanent impairment to a body structure or a body function.

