Note: This includes device deficiencies that might have led to a serious adverse event if (a) suitable action had not been taken or (b) intervention had not been made or (c) if circumstances had been less fortunate.

VIII. DATA MANAGEMENT

Data Collection Process

Data will be collected in an anonymous form using case report forms for each subject. CRFs will be transmitted to the data center for entry in to the database. Data may be collected by clinical research personnel assigned to the study, under the supervision of the investigator.

Data Confidentiality

Subject data will be collected in an anonymous form. Each site will keep a confidential, site – only log of enrolled patients connecting their identity to a coded subject identifier. Each subject will be entered on the log along with procedure date and will be assigned a patient study number comprised of the site number and sequential subject number enrolled. This coded number will be used in the CRFs. For example, John Q Doe, the 12th patient enrolled at site number 2, will be assigned study identifier 002-012. All activities will be performed in compliance with HIPAA and Good Clinical Practice standards

Data Center

CRFs or coded anonymized data will be forwarded to the Data Center at the Long Beach VA Medical Center, checked for completeness, and entered in the Database as received. Incomplete forms will be returned to the study site for completion. Electronic submission of Data may be employed, but is not required.

See the "Study Statistical Plan" for a description of the plan.

IX. ETHICAL, REGULATORY & ADMINISTRATIVE REQUIREMENTS

The devices being studied in this clinical plan, and the tests performed under it, are approved for marketing by the US-FDA for use as described and have been in use for TRA procedures at the participating institutions. FDA approval of the study is not required. No part of the study uses any device or test that is considered investigational.

Investigational Review Board Approvals.

Data from this study may be used for publication in the scientific literature, and therefore IRB approval is required. No patient may be enrolled until IRB approval is granted, and an Informed Consent approved by the IRB is signed by the subject.

Protocol Adherence and Amendments

Investigators will be required to adhere to the protocol requirements. Deviations or violations of the protocol may result in dismissal from the study.

Informed Consent

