A PROSPECTIVE RANDOMIZED STUDY COMPARING THE INCIDENCE OF RADIAL ARTERY OCCLUSION (RAO) AND THE TIME TO HEMOSTASIS (TTH) WHEN USING A HEMOSTASIS BAND ALONE AND IN CONJUNCTION WITH A DISC COMPRISED OF POTASSIUM FERRATE (STATSEAL ADVANCED) FOLLOWING TRANSRADIAL CATHETERIZATION. Study Sponsor: A Physician Initiated Study

Principal Investigator: [name], MPA

Cardiology Division Veterans Medical Center Long Beach

Statistical Analysis

Continuous data are presented as mean \pm standard deviation and as median [interquartile range], and compared using unpaired t-test and Mann-Whitney U-test, respectively. Discrete data are presented as frequencies with their respective percentages and compared using Fisher's exact test. Outcome data were analyzed on an intention-to-treat basis. Two-tailed tests of significance are reported and p values < 0.05 were considered statistically significant. Univariate logistic regression was performed using all baseline patient and procedural variables available to predict the secondary outcome of hematoma formation. Variables that were significant in univariate analysis at $p<0.25$ were retained and entered into a multivariate model with a threshold of $p<0.05$ being considered as significant. Statistical analyses were performed using the SPSS statistical software program (SPSS version 16.0.2, Chicago, IL).

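### The withdrawal rule excludes and replaces patients even after randomization, which contradicts the SAP's intention-to-treat analysis

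*Protocol*

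**What the plan says.** Protocol section IV, under End of Study Status / Effect of Withdrawals, lists two events that end a subject's participation. The first is completing treatment and all follow-up tests. The second is withdrawing consent, and there the rule is "Patients who withdraw from the study will be replaced and excluded from data analysis". No time limit is attached.

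Under Timing of Subject Enrollment in the same section, consent is taken before sedation, but randomization waits for a successful procedure. The text reads "When a patient is officially enrolled (after successful completion of a TRA procedure), the envelope corresponding to that patient number" in the log is then opened and the arm revealed.

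The SAP states "Outcome data were analyzed on an intention-to-treat basis". It names no exception for withdrawals, defines no analysis set and gives no rule for missing data.

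Three further statements fix what a patient may have contributed before withdrawing:

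- **Compression, StatSeal arm (SSA):** "After an additional 20 minutes (40 minutes after procedure), the TR band will be completely deflated".
- **Compression, control arm (TRB):** "The TR band will be left inflated and in place for 2 hours following the procedure for all patients", after which deflation attempts begin.
- **Last pulse-oximetry exam (section V, Test methodology):** "Within 30' of discharge or 24 hours post procedure", whichever is first.

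The primary safety outcome (section VI) covers "Any adverse event / complication at the vascular access site (e.g. Class III, IV, or V Hematoma" and other bleeding, over the same period up to discharge or 24 hours.

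**The concern.** Two analysts could follow the two documents faithfully and report different analysis sets: one drops a randomized patient whom the other keeps.

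The assignment is open once the envelope is read, and the arms differ in what the patient experiences. Scheduled full deflation is at 40 minutes in SSA, and deflation does not begin until 120 minutes in TRB. Withdrawals therefore need not be alike in the two arms. Replacing a withdrawn patient restores the count but not the comparison that randomization set up.

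The excluded patient may also have finished contributing to an outcome. Complications and radial artery occlusion (RAO) are at stake more than TTH, because a comparison of small counts can turn on one or two patients.

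**Working it through.** **1. Does the rule reach randomized patients?** The order of events is: consent; procedure; envelope opened and device placed; compression; full deflation; last exam at discharge or 24 hours. The rule sits in a list that defines the end of participation for any subject, and the other entry in that list is completion of all follow-up tests. Withdrawal can therefore fall anywhere between consent and the last exam. Nothing limits the rule to the stretch before the envelope is opened.

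**2. The two rules side by side.**

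| Withdrawal occurs | Protocol section IV | SAP | Conflict |
|---|---|---|---|
| Before envelope opened | Exclude, replace | Patient not randomized | No |
| After envelope, band still inflated | Exclude, replace | Keep in assigned arm; TTH incomplete | Yes |
| After full deflation, before last exam | Exclude, replace | Keep; TTH and earlier exams available | Yes |

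**3. The plan's own sample size.** Inputs from section VI: difference 60 min, SD 100 min, two-sided alpha 0.05, power 90%, total 120.

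- Normal approximation: n per arm = 2 × (1.960 + 1.282)² × (100/60)² = 58.4, so 59 per arm and 118 in total.
- t-test: n = 59.4, so 60 per arm and 120 in total. Power at 60 per arm is 90.3%.

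The stated figure reproduces. It was planned for time to removal of the band, which is not the same variable as TTH: the SSA band is deflated at 40 minutes and removed at 60. As a rough guide only, losing 3 values per arm (assumed) lowers the t-test power from 90.3% to 88.8% at 57 per arm. The number of patients is not the problem.

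**4. Illustration for TTH (assumed counts).** Suppose w of 60 patients in one arm are swapped for patients whose TTH differs by D minutes. The arm mean moves by w × D / 60. With D from 60 to 100:

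- w = 1: 1.0 to 1.7 min
- w = 3: 3 to 5 min
- w = 6: 6 to 10 min

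The planned difference is 60 minutes, so the TTH comparison is fairly robust.

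**5. Illustration for complications (assumed counts).** If 6 of 60 patients in one arm have a complication (10%), and 3 of those 6 withdraw and are replaced by event-free patients, the rate reads 3/60 (5%).

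For the test, compare 6/60 with 0/60. Fisher's two-sided p = 2 × C(60,6)/C(120,6) = 2 × 50,063,860/3,652,745,460 = 0.027. Swap one affected patient for an event-free one: 5/60 against 0/60 gives p = 2 × C(60,5)/C(120,5) = 2 × 5,461,512/190,578,024 = 0.057. In this constructed case one exclusion crosses the 0.05 threshold. It shows sensitivity and is not a forecast.

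**The case against.** The strongest reply is that the rule was meant only for patients who change their mind between consent and randomization. That would remove the conflict, but the text does not say so. If it is what was intended, a few words settle it.

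Several other points stand and limit the concern:

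- **Materiality is not shown.** The trigger is withdrawal of consent, observation lasts at most about a day, and no withdrawal rate is given. There may be few cases or none.
- **The remedy is partial for TTH.** A patient who withdraws with the band still inflated has no completed TTH under either rule. Longer compression in TRB is the most obvious reason for unequal withdrawal, and keeping such patients in the analysis set does not supply the missing value.
- **The record itself is not lost.** Section VII requires all adverse events to be recorded for the duration of the study. What can be lost is the patient's place in the between-arm comparison.
- **Consent may limit what can be kept.** The consent form was not available for this review.

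A reader might infer more than the documents support. One inference is that the trial is biased in a known direction because TRB patients are compressed longer. The schedule shows only that the arms differ, not who would withdraw. Another is that most late withdrawals would discard a finished TTH. For TRB the protocol gives only when deflation attempts start, not when they succeed, so that cannot be said. A third is that the trial would be underpowered. Replacement maintains the count, and even modest unreplaced losses cost little power.

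**Conclusion.** The rule is wrong as written. Applied after the envelope is opened, it contradicts the SAP's intention-to-treat statement, and no text in either document reconciles the two. It can remove from the comparison a randomized patient who already has a completed TTH, a pulse-oximetry result or a primary-safety complication.

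The size and direction of any bias are unknown and cannot be derived from the documents. Each excluded patient is 1/60 = 1.7% of an arm at the planned minimum. The conclusion rests on reading the withdrawal sentence as it stands, without a limit at randomization. It does not rest on the assumed counts in the illustrations. This should be fixed because the two rules give different analysis sets and the correction is cheap, not because a large distortion has been shown.

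**What to change.** - In protocol section IV, limit exclude-and-replace to patients who withdraw before the envelope is opened.
- Analyse every randomized patient in the assigned arm, using data collected up to withdrawal as far as the consent terms allow. The sponsor should confirm what those terms permit.
- Treat a TTH not completed at withdrawal as missing, and say plainly that the rule does not cure this part of the loss.
- Let added patients supplement, not displace, those who withdrew. Section VIII already has each subject "assigned a patient study number comprised of the site number and sequential subject number enrolled", and envelopes are tied to that number, so an added patient simply takes the next one.
- Report withdrawals by arm and timing.
- Repeat the rule in the SAP. The SAP is written in the past tense. If the analysis has been done, state which rule was applied and report any excluded randomized patients by arm.

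**Cost.** One sentence in the protocol and a short SAP paragraph, with no added visits. Keeping 120 patients with complete data would need 120/(1 − d) enrolled: 123, 127 or 134 for assumed losses d of 2%, 5% or 10%. All are within the maximum of 180. The downside is that a few randomized patients may lack a final TTH or RAO value, and the report will have to show those gaps.
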